8.3.7 Monitoring for SARS Cov-2 Exposure and COVID-19 Disease

As outlined in Section 4.2.1.3, this trial intends to identify potential exposures and confirmed infections by SARS-CoV-2 amongst study participants.

Study participants will be educated to recognize and report symptoms that may be related to SARS-CoV-2 infection and will be instructed to contact the site via phone in case of suspected SARS-CoV-2 infection (if severe symptoms are reported the participant will be instructed to seek urgent medical attention). The Investigator will facilitate the study participant receiving medical care as appropriate based on their clinical judgement, including arranging a nasopharyngeal PCR testing for acute disease. No more than 3 days should transpire between the subject contacting the clinical site and the arrangement of a medical care visit by the investigator.

Trial participants will be educated at regular intervals during in person visit to recognize and report the following potential SARS-CoV-2 symptoms based on current CDC guidance (<https://www.cdc.gov/coronavirus/2019-ncov/symptoms-testing/symptoms.html>).

- Fever or chills
- Cough

- Shortness of breath or difficulty breathing
- Fatigue
- Muscle or body aches
- Headache
- New loss of taste or smell
- Sore throat
- Congestion or runny nose
- Nausea or vomiting
- Diarrhea

The Investigator will endeavor to collect detailed data on confirmed COVID-19 cases including the onset of specific symptoms, duration of symptoms, hospitalization (if any), and COVID-19 will be classified as severe or non-severe based on the FDA's "Development and Licensure of Vaccines to Prevent COVID-19, Guidance for Industry"

For the purposes of this study, a virologically confirmed SARS-CoV-2 infection is defined as any study participant with positive SARS-CoV-2 PCR test.

Severe COVID-19 is defined as:

Virologically confirmed SARS-CoV-2 infection with any of the following:

- Clinical signs at rest indicative of severe systemic illness (respiratory rate ≥ 30 per minute, heart rate ≥ 125 per minute, SpO₂ $\leq 93\%$ on room air at sea level or PaO₂/FiO₂ < 300 mm Hg)
- Respiratory failure (defined as needing high-flow oxygen, noninvasive ventilation, mechanical ventilation or ECMO)
- Evidence of shock (SBP < 90 mm Hg, DBP < 60 mm Hg, or requiring vasopressors)
- Significant acute renal, hepatic, or neurologic dysfunction
- Admission to an ICU
- Death

This clinical trial is not intended to interfere with local health practices and regulations regarding the management of confirmed or suspected SARS-CoV-2 infections or COVID-19 disease. The main role of the Investigator to help study participants to receive all appropriate

medical care according to local health practices and regulations. Study participants may be tested as appropriate according to local regulations and will receive any required medical care within their existing healthcare systems. However if a subject is not administered a nasopharyngeal PCR test for SARS-CoV-2 according to local regulations and the Investigator feels it is warranted, then they may directly arrange for SARS-CoV-2 PCR testing as available by nasopharyngeal swab.

If a subject is suspected/diagnosed with an actual COVID-19 infection they will not receive any subsequent study vaccination but should endeavor to perform all visits for safety follow-up that they are safely able to attend in person as allowed according to local regulations.

Exposure to known SARS CoV-2 infected patients and SARS-CoV-2 infection, and COVID-19 disease, will be captured as ECIs as documented in Section 8.4.7.

8.3.8 Clinical Safety Laboratory Assessments

Refer to Appendix 2 for the list of clinical laboratory tests to be performed and to the SoA for the timing and frequency.

The investigator or medically qualified designee (consistent with local requirements) must review the laboratory report, document this review, and record any clinically relevant changes occurring during the study in the AE section of the CRF. The laboratory reports must be filed with the source documents. Clinically significant abnormal laboratory findings are those which are not associated with the underlying disease, unless judged by the investigator to be more severe than expected for the participant's condition.

All protocol-required laboratory assessments, as defined in Appendix 2, must be conducted in accordance with the laboratory manual and the SoA.

If laboratory values from nonprotocol-specified laboratory assessments performed at the institution's local laboratory require a change in study participant management or are considered clinically significant by the investigator (eg, SAE or AE or dose modification), then the results must be recorded in the appropriate CRF (eg, SLAB).

For any laboratory tests with values considered clinically significantly abnormal during participation in the study or within 28 days after the last dose of study intervention, every attempt should be made to perform repeat assessments until the values return to normal or baseline or if a new baseline is established as determined by the investigator.

8.4 Adverse Events, Serious Adverse Events, Medically-Attended Adverse Events and Other Reportable Safety Events

The definitions of an AE, SAE, or MAAE as well as the method of recording, evaluating, and assessing causality of AE, SAE and MAAE and the procedures for completing and transmitting AE, SAE, MAAE and other reportable safety event reports can be found in Appendix 3.

Adverse events, SAEs, MAAEs, and other reportable safety events will be reported by the participant (or, when appropriate, by a caregiver, surrogate, or the participant's legally authorized representative).

The investigator and any designees are responsible for detecting, documenting, and reporting events that meet the definition of an AE, SAE or MAAE as well as other reportable safety events. Investigators remain responsible for following up AEs, SAEs, MAAEs, and other reportable safety events for outcome according to Section 8.4.3.

The investigator, who is a qualified physician, will assess events that meet the definition of an AE, SAE or MAAE as well as other reportable safety events with respect to seriousness, intensity/toxicity and causality.

8.4.1 Time Period and Frequency for Collecting AE, SAE, MAAE, and Other Reportable Safety Event Information

AEs, SAEs, MAAEs, and other reportable safety events that occur after the participant provides documented informed consent form, but before intervention allocation/randomization, must be reported by the investigator for randomized participants only if the event is the result of a protocol-specified intervention, including but not limited to washout or discontinuation of usual therapy, diet, placebo, or a procedure.

From the time of vaccination all AEs must be reported by the investigator up to 28 days after any study vaccination. SAEs, MAAEs, ECIs, arthralgia of any grade and other reportable safety events must be reported by the investigator from the time of vaccination through the end of study visit.

Additionally, any SAE brought to the attention of an investigator any time outside of the time period specified in the previous paragraph also must be reported immediately to the Sponsor if the event is considered related to study intervention.

Investigators are not obligated to actively seek AEs or SAEs or other reportable safety events in former study participants. However, if the investigator learns of any SAE, including a death, at any time after a participant has been discharged from the study, and he/she considers the event to be reasonably related to the study intervention or study participation, the investigator must promptly notify the Sponsor.

All initial and follow-up AEs, SAEs, MAAEs, and other reportable safety events will be recorded and reported to the Sponsor or designee within the time frames as indicated in [Table 5](#).

Table 5 Reporting Time Periods and Time Frames for Adverse Events and Other Reportable Safety Events

Type of Event	Reporting Time Period: Consent to Randomization/ Allocation (Randomized participants only)	Reporting Time Period: Randomization/ Allocation through Protocol-specified Follow-up Period	Reporting Time Period: After the Protocol-specified Follow-up Period	Time Frame to Report Event and Follow-up Information to Sponsor:
NSAE	Report if: - due to protocol-specified intervention - causes exclusion - participant is receiving placebo run-in or other run-in treatment	Report all	Not required	Per data entry guidelines
SAE	Report if: - due to protocol-specified intervention - causes exclusion - participant is receiving placebo run-in or other run-in treatment	Report all	Report if: - drug/vaccine related. (Follow ongoing to outcome)	Within 24 hours of learning of event
MAAEs	Report if: - due to intervention - causes exclusion	Report all	Not required	Within 5 days of learning of event
Pregnancy/ Lactation Exposure	Report if: - participant has been exposed to any protocol-specified intervention (eg, procedure, washout or run-in treatment including placebo run-in)	Report all	Previously reported – Follow to completion/termination; report outcome	Within 24 hours of learning of event
ECI (require regulatory reporting)	Report if: - due to intervention - causes exclusion	Report all - require regulatory reporting	Not required	Within 24 hours of learning of event
ECI (do not require regulatory reporting)	Report if: - due to intervention - causes exclusion	Report - non-DILI ECIs and those not requiring regulatory reporting	Not required	Within 5 calendar days of learning of event
Cancer	Report if: - due to intervention - causes exclusion	Report all	Not required	Within 5 calendar days of learning of event (unless serious)
Overdose	Report if: - receiving placebo run-in or other run-in medication	Report all	Not required	Within 24 hours of learning of event

DILI=drug-induced liver injury; ECI=event of clinical interest; NSAE=nonserious adverse event; SAE=serious adverse event

8.4.2 Method of Detecting AEs, SAEs, MAAEs, and Other Reportable Safety Events

Care will be taken not to introduce bias when detecting AEs and/or SAEs and other reportable safety events. Open-ended and nonleading verbal questioning of the participant is the preferred method to inquire about AE occurrence.

8.4.3 Follow-up of AE, SAE, MAAE, and Other Reportable Safety Event Information

After the initial AE/SAE/MAAE report, the investigator is required to proactively follow each participant at subsequent visits/contacts. All AEs, SAEs, MAAEs and other reportable safety events, including pregnancy and exposure during breastfeeding, ECIs, cancer, and overdose will be followed until resolution, stabilization, until the event is otherwise explained, or the participant is lost to follow-up (as defined in Section 7.3). In addition, the investigator will make every attempt to follow all nonserious AEs that occur in randomized participants for outcome. Further information on follow-up procedures is given in Appendix 3.

8.4.4 Regulatory Reporting Requirements for SAE

Prompt notification (within 24 hours) by the investigator to the Sponsor of SAE is essential so that legal obligations and ethical responsibilities towards the safety of participants and the safety of a study intervention under clinical investigation are met.

The Sponsor has a legal responsibility to notify both the local regulatory authority and other regulatory agencies about the safety of a study intervention under clinical investigation. The Sponsor will comply with country-specific regulatory requirements and global laws and regulations relating to safety reporting to regulatory authorities, IRB/IECs, and investigators.

Investigator safety reports must be prepared for SUSARs according to local regulatory requirements and Sponsor policy and forwarded to investigators as necessary.

An investigator who receives an investigator safety report describing an SAE or other specific safety information (eg, summary or listing of SAE) from the Sponsor will file it along with the IB and will notify the IRB/IEC, if appropriate according to local requirements.

8.4.5 Pregnancy and Exposure During Breastfeeding

Although pregnancy and infant exposure during breastfeeding are not considered AEs, any pregnancy or infant exposure during breastfeeding in a participant (spontaneously reported to the investigator or their designee) that occurs during the study are reportable to the Sponsor.

All reported pregnancies must be followed to the completion/termination of the pregnancy. Pregnancy outcomes of spontaneous abortion, missed abortion, benign hydatidiform mole, blighted ovum, fetal death, intrauterine death, miscarriage, and stillbirth must be reported as

serious events (Important Medical Events). If the pregnancy continues to term, the outcome (health of infant) must also be reported.

8.4.6 Disease-related Events and/or Disease-related Outcomes Not Qualifying as AEs or SAEs

This is not applicable.

8.4.7 Events of Clinical Interest

Selected serious and nonserious AEs are also known as ECIs and must be reported to the Sponsor.

Events of clinical interest for this study include:

1. An overdose of Sponsor's product, as defined in Section 8.5.
2. Any laboratory confirmed diagnosis of SARS-CoV-2 infection (virologically confirmed by PCR) and any resulting clinical sequelae will be reported as an ECI in study participants throughout the duration of the study. See Section 8.3.7 for further details.
3. Known exposure to a confirmed case of active SARS-CoV-2, defined as individual who has had close contact (< 1.5 meters for ≥ 15 minutes), will be reported as an ECI in study participants throughout the duration of the study
4. AEs \geq Grade 3 reported as a solicited AE on the VRC
5. Acute respiratory distress syndrome (ARDS)
6. Pneumonitis
7. Acute cardiac injury
8. Arrhythmias
9. Septic shock-like syndrome
10. Acute kidney injury
11. Vasculitis
12. New onset Autoimmune disease (AID)
13. Meningitis
14. Atypical measles
15. Anosmia

16. Dysgeusia
17. Encephalitis
18. Encephalopathy
19. Clinically significant arthralgias

The investigator should report all ECIs for the whole period of the study.

8.4.8 Adverse Events Reported on the VRC

Participants will use a VRC to report solicited and unsolicited AEs.

The definitions of solicited and unsolicited AEs can be found in Appendix 3.

8.4.8.1 Solicited Adverse Event

Solicited AEs for this study are summarized in [Table 6](#).

Table 6 Solicited Adverse Events for Protocol

Type of Solicited Adverse Event	Predefined Solicited Adverse Events	Solicited Time Period
Injection site	
 ○ Injection-site pain/tenderness ○ Injection-site swelling ○ Injection-site redness/erythema 	For the first 5 days after each study intervention 
 ○ For 1-dose panels: Day 1 to Day 5 ○ For 2-dose Day 1 Day 57 panels: Day 1 to Day 5 and Day 57 to Day 61 ○ For 2-dose Day 1 Day 169 panels: Day 1 to Day 5 and Day 169 to Day 173
Systemic	
 ○ Muscle pain/myalgia ○ Joint pain/arthralgia ○ Headache ○ Fatigue/Tiredness ○ Rash ○ Nausea ○ Fever 	For the first 14 days after each study intervention 
 ○ For 1-dose panels: Day 1 to Day 14 ○ For 2-dose Day 1 Day 57 panels: Day 1 to Day 14 and Day 57 to Day 71 ○ For 2-dose Day 1 Day 169 panels: Day 1 to Day 14 and Day 169 to Day 183

All solicited injection-site AEs will be considered related to study intervention. The investigator will assess all solicited injection-site AEs for toxicity, and all solicited systemic AEs for both toxicity and causality (Appendix 3).

In addition, the investigator will review all solicited AEs for the following:

- Is the event a symptom of another diagnosis?
- Is the event ongoing at the end of the solicited period?
- Does the event meet serious criteria?

A solicited AE that meets any of the above criteria must also be reported on the appropriate eCRF as specified in the data entry guidelines.

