1.3.2 SoA for 2-Dose Panels (Day 1, Day 57)

2-dose Day 1, Day 57-Panels A-B and I-J															
	Screening	Study Day												Post-Study	Notes
Scheduled Hour, Day, Week, etc.	Screening -28 to -1 ^b	Day 1 Pre-dose	1	2 ^a	8±1	15±1	29±3	57±3	58 ^a	71±1	85±3	115±7	211±14	422±14	Section 8.11.5 Details on variance in procedure collection times
Administrative Procedures															
Informed Consent	X														Section 8.1.1.1
Informed Consent for Future Biomedical Research	X														Section 8.1.1.2
Demographics	X														
Inclusion/Exclusion Criteria	X	X						X							Section 5.0
Participant ID Card	X														Section 8.1.3
Medical History & Vaccination History	X														Section 8.1.4
Prior/Concomitant Medication Review	X	X	X	X	X	X	X	X	X	X	X	X	X	X	Sections 6.6, 8.1.5 Including Non-study Vaccination Review
Assignment of Screening Numbers	X														Section 8.1.6
Assignment of Randomization Number		X													Sections 5.5 and 8.1.7
COVID-19 Symptoms Training		X			X	X	X		X	X	X	X			Section 8.3.7
V591/Placebo Administration			X					X							Section 8.1.8
Clinical Procedures/ Safety Assessment															
Full physical examination	X	X											X	X	Section 8.3.1.1

2-dose Day 1, Day 57-Panels A-B and I-J															
	Screening	Study Day												Post-Study	Notes
Scheduled Hour, Day, Week, etc.	Screening -28 to -1 ^b	Day 1 Pre-dose	1	2 ^a	8±1	15±1	29±3	57±3	58 ^a	71±1	85±3	115±7	211±14	422±14	
Symptoms driven physical exam			X		X	X	X	X		X	X	X			Section 8.3.1.2 Only to be conducted if participant symptoms warrant an exam or at investigator's discretion
Targeted physical examination of injection site			X		X	X		X		X					Section 8.3.1.3 Panels A and B: ~ 8 hours after vaccination on Day 1 and Day 57. Panels I and J: ~ 1 hour after vaccination on Day 1 and Day 57.
Height	X														Section 8.3.1.4
Weight	X							X						X	Section 8.3.1.4
Semi-recumbent Vital Signs (Blood Pressure [BP] and Heart Rate [HR] and Respiratory Rate [RR])	X	X	X		X	X	X	X		X	X	X	X	X	Section 8.3.2 Day 1 predose: within ~ 3 hours of dosing. Panels A and B Postdose: ~ 8 hours after vaccination on Day 1 and Day 57. Panels I and J Postdose: ~ 1 hour after vaccination on Day 1 and Day 57.
Body Temperature	X	X	X	X	X	X	X	X	X	X	X	X	X	X	Section 8.3.2.2 (temperature) and Section 8.3.5 (VRC) Days 1 to 14 and Days 57 to 70 will be done by participant and recorded on the VRC. All other measurements will be done by clinic staff.

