1.3.3 SoA for 2-Dose Panels (Day 1, Day 169)

2-dose Day 1, Day 169-Panels F and K-L														
	Screening	Study Day											Post-Study	Notes
Scheduled Hour, Day, Week, etc.	Screening -28 to -1	Day 1 Pre-dose	1	2 ^a	8±1	15±1	29±3	85±3	169±3	170 ^a	197±3	365±7	534±14	Section 8.11.5 Details on variance in procedure collection times
Administrative Procedures														
Informed Consent	X													Section 8.1.1.1
Informed Consent for Future Biomedical Research	X													Section 8.1.1.2
Demographics	X													
Inclusion/Exclusion Criteria	X	X							X					Section 5.0
Participant ID Card	X													Section 8.1.3
Medical History & Vaccination History	X													Section 8.1.4
Prior/Concomitant Medication Review	X	X	X	X	X	X	X	X	X	X	X	X	X	Sections 6.6, 8.1.5 Including Non-study Vaccination Review
Assignment of Screening Numbers	X													Section 8.1.6
Assignment of Randomization Number		X												Sections 5.5 and 8.1.7
COVID-19 Symptoms Training		X			X	X	X	X		X	X			Section 8.3.7
V591/Placebo Administration			X						X					Section 8.1.8
Clinical Procedures/ Safety Assessment														
Full physical examination	X	X											X	Section 8.3.1.1
Symptoms driven physical exam			X		X	X	X	X	X		X			Section 8.3.1.2 Only to be conducted if participant symptoms warrant an exam or at investigator's discretion
Targeted physical examination of injection site			X		X	X			X					Section 8.3.1.3 At ~ 1 hour postdose on Day 1 and Day 169

2-dose Day 1, Day 169-Panels F and K-L															
	Screening	Study Day											Post-Study	Notes	
Scheduled Hour, Day, Week, etc.	Screening -28 to -1	Day 1 Pre-dose	1	2 ^a	8±1	15±1	29±3	85±3	169±3	170 ^a	197±3	365±7	534±14		
Height	X														Section 8.3.1.4
Weight	X								X				X		Section 8.3.1.4
Semi-recumbent Vital Signs (Blood Pressure [BP] and Heart Rate [HR] and Respiratory Rate [RR])	X	X	X		X	X	X	X	X		X	X	X		Section 8.3.2 Day 1 predose measurements will be done within ~ 3 hours of dosing. Day 1 and Day 169: Postdose measurements will be taken ~ 1 hour after vaccination.
Body Temperature	X	X	X	X	X	X	X	X	X	X	X	X	X		Section 8.3.2.2 (temperature) and Section 8.3.5 (VRC) Days 1 to 14 and Days 169 to 182 will be done by participant and recorded on the VRC. All other measurements will be done by clinic staff.
12-lead ECG	X	X													Section 8.3.3 Day 1 predose ECG will be done within 24 hours of dosing.
Distribute Paper Vaccination Report Card (VRC)			X						X						

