8.3.2.2 Body Temperature

Body temperature should be measured orally and recorded as single measurements per timepoint. The same method must be used for all measurements for each individual participant and should be the same for all participants.

Oral temperature will be assessed before study vaccine is administered on Day 1. If the participant has a fever (defined as an oral temperature of $\geq 100.4^{\circ}\text{F}$ or $\geq 38.0^{\circ}\text{C}$) within the 1 week period prior to receiving a study vaccination, the participant should not receive the study vaccine. The Day 1 vaccination may be rescheduled for a time when fever is resolved.

Postvaccination, if an oral temperature indicates a fever (defined as an oral temperature of $\geq 38.0^{\circ}\text{C}$ or 100.4°F), then an AE of “fever” must be documented in the eCRF.

For measurements to be collected on the VRC on Days 1-14 and Days 57-70 or Days 169-182 (2-dose panels only), participants will be provided an oral thermometer. For sentinel panels (Panels A and B), Day 1 and Day 57 postdose measurements will be done approximately 8 hours (± 15 min). For Panel E, Day 1 postdose measurements will be done approximately 8 hours (± 15 min) for at a minimum the first 5 subjects in the Panel. The rest of the participants in panel E will be monitored for at least 1 hour (± 15 min) after vaccination. The Day 1, and Day 57 or Day 169 (2-dose panels only) postdose measurement for all other panels will be done approximately 1 hour (± 15 min). The Day 1, and Day 57 or Day 169 (2-dose panels only) postdose measurement will be measured and recorded by the participants on the VRC, under observation by the clinic staff. All the other measurements on the VRC and will be done by the participant without supervision. See Section 8.3.5.

All other temperature measurements listed on the SoA that are not on the VRC will be done by clinic staff on the CRU source documents.

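### Table 6 lists a 15-day solicited systemic AE window after dose 2, against its own 14-day statement and the primary endpoint definition

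*Combined protocol and SAP*

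**What the plan says.** In Section 8.4.8.1, Table 6, the systemic row opens with a stated length: "For the first 14 days after each study intervention". The day ranges below it are Day 1 to Day 14 for the 1-dose panels, then "For 2-dose Day 1 Day 57 panels: Day 1 to Day 14 and Day 57 to Day 71" and "For 2-dose Day 1 Day 169 panels: Day 1 to Day 14 and Day 169 to Day 183". The injection-site row of the same table, for the Day 57 panels, reads "Day 1 to Day 5 and Day 57 to Day 61".

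Elsewhere the period is 14 days:

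- Sections 1.1 and 3 define the primary endpoint as solicited systemic events on days 1 to 14 after any dose. Sections 9.1, 9.4.1 and 9.6.1, including Table 9, repeat it.
- The Schedule of Activities for the Day 57 panels (Section 1.3.2) says of temperature: "Days 1 to 14 and Days 57 to 70 will be done by participant and recorded on the VRC". For the Day 169 panels (Section 1.3.3) it says: "Days 1 to 14 and Days 169 to 182 will be done by participant and recorded on the VRC". Section 8.3.2.2 gives the same ranges. Fever is one of the systemic terms in Table 6.

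For the 2-dose panels, Section 9.6.1 also plans safety summaries after each dose separately.

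**The concern.** Table 6 is the only place that turns the solicited systemic period into study days for all the systemic terms, and its second-dose entries run a day past the period it states. Nothing says whether Table 6 or the endpoint text governs.

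Three things depend on the answer:

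- **By-dose summaries.** If the table is programmed literally, the dose-1 and dose-2 columns cover windows of different length.
- **Labelling.** An onset on the extra day is solicited under Table 6 and unsolicited under the endpoint definition. The label matters because Section 8.4.7 makes solicited report-card events of Grade 3 or higher events of clinical interest. Section 8.4.8.1 also requires extra reporting for events still ongoing when the solicited period ends.
- **Fever.** Table 6 solicits it for one day more than the participant's own temperature record runs.

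**Working it through.** **Step 1: count the days.** Inclusive length = end − start + 1, with the vaccination day as day 1.

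| Window | Source | After dose 1 | Day 57 dose | Day 169 dose | Stated length |
|---|---|---|---|---|---|
| Injection site | Table 6 | 1–5: 5 | 57–61: 5 | 169–173: 5 | 5 |
| Report-card temperature | 1.3.2, 1.3.3, 8.3.2.2 | 1–14: 14 | 57–70: 14 | 169–182: 14 | – |
| Nonserious AEs | 1.3.2, 1.3.3 | 1–28: 28 | 57–84: 28 | 169–196: 28 | 28 |
| **Solicited systemic** | **Table 6** | **1–14: 14** | **57–71: 15** | **169–183: 15** | **14** |

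The plan's 14 days is reproduced after dose 1 and not after dose 2. Only these two entries depart from the pattern.

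**Step 2: try the other convention.** With the vaccination day as day 0, length = end − start. The second-dose windows become 71 − 57 = 14 and 183 − 169 = 14, but the first becomes 14 − 1 = 13. The row is unequal either way. Day 71 is dose day + 14, which corresponds to Day 15 after dose 1, not Day 14.

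**Step 3: who is affected.** From Tables 3 and 4, the 2-dose panels are A and B (4 V591 + 1 placebo each) and F, I, J, K and L (20 + 5 each).

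- V591: 4 + 4 + 5 × 20 = 108
- Placebo: 1 + 1 + 5 × 5 = 27
- Check against Table 12: 24 + 24 + 20 + 20 + 20 = 108, and 12 + 15 = 27

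**Step 4: extra time at risk.**

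- Per second dose: 15/14 − 1 = 7.1%.
- Over the trial, with 260 planned participants and 135 second doses: 260 × 14 + 135 × 14 = 5,530 person-days under the endpoint definition, against 260 × 14 + 135 × 15 = 5,665 under Table 6. The increase is 135/5,530 = 2.4%.

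**Step 5: effect on a dose-2 incidence.** The documents give no event rate for V591, so this step rests on an assumption. With a constant daily hazard and 14-day risk r, the 15-day risk is 1 − (1 − r)^(15/14).

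| Assumed 14-day risk | 15-day risk | Difference, points |
|---|---|---|
| 10% | 10.7% | 0.7 |
| 20% | 21.3% | 1.3 |
| 35% | 37.0% | 2.0 |

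If onsets cluster soon after the dose, the last day adds less than this.

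**Step 6: nominal against actual days.** Dose 2 may be given within ±3 days (Section 8.11.5, Table 7, and the Schedules of Activities). For a dose on Day 58, 59 or 60, study Day 71 is day 14, 13 or 12 after that dose, counting the dose day as day 1, and so lies inside a 14-day window. For a dose on Day 54, 55 or 56, study Day 70 is day 17, 16 or 15 and lies outside it. A window fixed in nominal study days is therefore wrong for anyone not dosed exactly on schedule.

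**The case against.** The strongest reply is that two stray table entries are outweighed by everything else. The endpoint definition, the SAP and Table 6's own opening line all say 14 days, and stopping rule 5 in Section 6.7.1 also refers to a 14-day period. A careful programmer would use 14. Participants complete the report card daily to Day 28 after each vaccination (Section 8.3.5), so no event is lost and only one day's label is in question. This stands as a limit on the consequences. It does not remove the contradiction.

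A reader might go further than the documents allow in four ways:

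- **That the primary endpoint is counted over unequal windows.** That follows only if Table 6 is programmed as written. No section says that the report card or the endpoint derivation is built from Table 6.
- **That the Day 71 visit adds staff-prompted reports after dose 2.** Staff review the card at Day 15 as well as Day 71, so contact is similar after both doses. Panels F, K and L (75 of the 135 participants) have no Day 183 visit.
- **That a planned dose-1 versus dose-2 comparison is biased.** Section 9.6.1 plans separate summaries by dose, not a contrast between doses. The planned confidence intervals are for differences between treatments.
- **That fever goes unmeasured on the extra day throughout.** The Day 57 panels have a clinic temperature at the Day 71 visit. Only for the Day 169 panels is no measurement scheduled on Day 183. The Day 57–70 and 169–182 ranges are stated for temperature alone; for the other systemic terms the conflict is with the 14-day definition.

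**Conclusion.** Table 6 is wrong as written: its second-dose systemic entries span 15 days where the table, the primary endpoint and the SAP say 14. If it is programmed literally, the dose-2 window is one day (7.1%) longer than the dose-1 window in the by-dose summaries. Over assumed 14-day risks of 10% to 35% and a constant daily hazard, that is about 0.7 to 2.0 percentage points.

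The 108 V591 and 27 placebo participants are the planned maximum. Amendment 04 ends the study with follow-up to at least Day 56, and the documents do not say how many second doses were given.

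V591 and placebo share the same window within each panel, so the extra day does not bias the randomised comparison. No sample-size or power figure changes. This is a minor correction, worth making because it concerns a primary endpoint and the final analysis still needs one window for whatever dose-2 data exist.

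**What to change.** Change the Table 6 systemic entries to end at Day 70 (Day 57 panels) and Day 182 (Day 169 panels). In the analysis specification, derive the solicited systemic window for every participant and every dose as actual dose date through dose date + 13 days, and class onsets after that as unsolicited. The rule should not relabel every onset on nominal Day 71 or Day 183, because the ±3-day dosing window puts some of those days inside a participant's own 14 days.

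The cost is two table entries and one derivation line. No visit, sample or dose changes.
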